##### Arm 1 versus Arm C

We will estimate the geometric mean ratio for each PK parameter (Cmin, Cmax, Tmax, AUC0-24h) together with the 90% confidence interval using available data in the alive/adequate treatment set.

This non-compartmental analysis will be in conjunction with non-linear mixed-effects modeling to estimate the primary PK parameters (e.g., apparent oral clearance (CL/F), volume of distribution, rate of absorption). The model-based analysis will use the intensive PK samples as well as the sparse samples collected throughout the study period and all protein concentration data. We will model the PK observations continuously over time, taking in account each participant's actual dosing history. We will conduct a covariate analysis to evaluate the potential impact of demographics and concomitant medications. We will compare the derived secondary metrics with the non-compartmental analysis results in a posterior predictive check.

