We will report the minimum concentration (Cmin), maximum concentration (Cmax), time of Cmax (Tmax), and area under the concentration curve (AUC0-24h) estimated through non-compartmental analysis for weeks 2 and 13 summarized separately.

Arm C

We will report the estimated minimum concentration (Cmin), maximum concentration (Cmax), time of Cmax (Tmax), and area under the concentration curve (AUC0-24h) estimated through non-compartmental analysis for week 2.

Arm 1 versus Arm C

We will compare the estimated minimum concentration (Cmin), maximum concentration (Cmax), time of Cmax (Tmax), and area under the concentration curve (AUC0-24h) at week 2 between Arm 1 and Arm C intensive PK participants. We will estimate the geometric mean ratio comparing Arm 1 to Arm C and corresponding 90% confidence interval. As a supplemental analysis, we will use a Wilcoxon rank sum test and report the p-value.

3.2.12 Change from baseline in skin pigmentation (colorimetric L\*, a\*, b\* parameters) utilizing ambient light-independent reflectance mapping at weeks 8, 13, 26, and 65.

Mean change in total color difference from week 0 to each of weeks 8, 13, 26, 65 in Arm 1 vs Arm 2 at each of the following locations; (1) left cheek, (2) right cheek, (3) forehead, (4) chin.

Mean change in total color difference from week 0 to each of weeks 8, 13, 26, 65 in Arm 1 vs Arm 2 using, for each participant, the location with the maximum change.

3.2.13 Change from baseline in participant-reported changes in skin pigment and distress related to perceived skin hyperpigmentation at weeks 8, 13, 26, and 65.

Mean subjective 'change in coloration' score between week 0 and weeks 8, 13, 26, and 65 in Arm 1 vs Arm 2 (10-point numeric rating scale where 0=none, 10=most significant possible).

Mean subjective 'distress related to skin coloration' score at each of weeks 0, 8, 13, 26, and 65 in Arm 1 vs Arm 2 (10-point numeric rating scale where 0=none, 10=worst possible)

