#### **5.1.3.10 Plasma Pharmacokinetic Parameters for CFZ (Objectives 2.3.2.10 and 2.3.2.11; Outcome Measures 3.2.11)**

[name] and team at Radboudumc, The Netherlands, will conduct this analysis.

The PK parameters of interest (Cmin, Cmax, Tmax, AUC0-24h) for CFZ in Arm 1 and Arm C of the alive/adequate treatment set will be estimated using non-compartmental methods applied to concentrations from intensive PK sampling visits. The AUC will be determined using the trapezoidal rule. Cmin will be the minimum observed concentration after the observed dose. Cmax will be the maximum observed concentration. Tmax is the time at which Cmax occurs.

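### For Tmax, the only Arm 1 v Arm C estimate planned is a geometric mean ratio, which suits a sampling time poorly and is undefined if any Tmax is zero; a rank-based difference in hours would serve better

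*SAP*

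**What the plan says.** SAP 5.1.3.10, under Arm 1 versus Arm C, applies one estimator to all four non-compartmental parameters: "We will estimate the geometric mean ratio for each PK parameter (Cmin, Cmax, Tmax, AUC0-24h", each with a 90% confidence interval. SAP 3.2.11 sets the same comparison at week 2 among intensive PK participants ("We will estimate the geometric mean ratio comparing Arm 1 to Arm C and corresponding 90% confidence interval") and adds one rank-based step: "As a supplemental analysis, we will use a Wilcoxon rank sum test and report the p-value". Section 5.1.3.10 does not repeat that test.

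Three definitions in SAP 5.1.3.10 matter here:

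- Tmax: "Tmax is the time at which Cmax occurs".
- Cmax: "Cmax will be the maximum observed concentration".
- Cmin: "Cmin will be the minimum observed concentration after the observed dose".

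Only Cmin is limited to samples after the dose.

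SAP 3.2.11 also reports Tmax within each arm (Arm 1 at weeks 2 and 13, Arm C at week 2) without naming a summary statistic. SAP 2.3 says that objectives other than primary efficacy will be presented as estimates with two-sided confidence intervals.

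**The concern.** A geometric mean ratio is natural for concentrations and AUC, which are positive, continuous and usually skewed on the raw scale. Tmax is a clock time read from the sample with the highest concentration. It takes only the values at which blood was drawn, and readers want its difference in hours rather than as a ratio.

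The ratio also needs the logarithm of every value. A participant whose highest concentration is in a pre-dose sample has a Tmax of 0, which has no logarithm. The analyst would then have to substitute a value or leave the participant out, and the SAP says nothing about either.

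At stake is the Tmax line of the loading-dose comparison (secondary objective 2.3.2.11). Its only between-arm estimate could turn on a choice made after the data are seen.

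**Working it through.** The SAP gives no sample size, standard deviation or interval width for the PK comparison, so there is no figure of its own to reproduce.

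**Inputs from the SAP.** Arm C is planned at about 20 (SAP 2.4). Participants who consent to intensive PK are randomized 2:1:1 to Arms 1, 2 and C (SAP 2.1), which gives about 40 in Arm 1 for 20 in Arm C. The numbers reached at early closure are not given.

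**Assumptions, not from the documents.** A typical Tmax of 5 h; substitutes of 0.5, 0.1 or 0.01 h for a zero; post-dose samples at 1, 2, 3, 4, 5, 6, 8, 12 and 24 h; a log-scale standard deviation of 0.5.

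**1. Is a zero possible?** The supplied text has no intensive sampling times, so this is inference. Cmin is limited to post-dose samples, but Cmax and Tmax are not. A trapezoidal AUC from 0 to 24 h needs a concentration at or near time 0. At week 2 of daily dosing, the pre-dose concentration is not expected to be nil. A zero is therefore not excluded, but it is not shown to occur.

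**2. How likely is at least one zero?** If each participant has probability p of a zero, the chance of at least one among N is 1 − (1 − p)^N.

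| p (assumed) | N = 60 (40 + 20) | N = 18 (12 + 6, assumed) |
|---|---|---|
| 0.02 | 70% | 30% |
| 0.05 | 95% | 60% |
| 0.10 | 99.8% | 85% |

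**3. What does one zero do to the estimate?** Replacing 5 h by f in one of n Arm C participants multiplies the Arm 1 to Arm C ratio by (5/f)^(1/n).

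| f (h) | n = 20 | n = 10 (assumed) |
|---|---|---|
| 0.5 | 10^(1/20) = 1.12 | 1.26 |
| 0.1 | 50^(1/20) = 1.22 | 1.48 |
| 0.01 | 500^(1/20) = 1.36 | 1.86 |

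**4. What does it do to the interval?** Without a zero, the 90% half-width on the log scale is 1.645 × 0.5 × √(1/40 + 1/20) = 0.225, a factor of 1.25. If the altered value sat at the Arm C log mean, the Arm C variance rises from 0.25 by [ln(5/f)]²/20.

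- f = 0.5: 0.25 + 2.303²/20 = 0.515. Half-width 1.645 × √(0.25/40 + 0.515/20) = 0.294, a factor of 1.34.
- f = 0.01: 0.25 + 6.215²/20 = 2.181. Half-width 1.645 × √(0.25/40 + 2.181/20) = 0.559, a factor of 1.75.

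Both the estimate and its precision therefore depend on the substitute.

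**5. Does the interval fail when every Tmax is positive?** Right-skewed Tmax values at the assumed sampling times were simulated, with 20,000 trials per setting and a Welch 90% interval on log Tmax. Coverage was 90.2% (40 v 20), 90.2% (20 v 10) and 90.3% (12 v 6). Discreteness alone did not harm it.

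**6. Late but positive values.** One Arm C participant at 24 h instead of 5 h moves the Arm C geometric mean by (24/5)^(1/20) = 1.08. Two move it by 1.17. Both lie inside the 1.25 half-width from step 4.

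**The case against.** The strongest defence is that a reader might call the planned Tmax ratio and interval invalid, and the documents do not support that. With positive values, the ratio is well defined and coverage was nominal under the assumptions above. An extreme late value moves it by less than its sampling error at the planned size. That part of the defence stands in full.

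Other strong readings also fail:

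- **That Tmax will be zero for someone.** The protocol text supplied is a letter of amendment without the PK sampling schedule. SAP 1.1 places coding detail in a separate Analysis Implementation Plan, and an outside PK group runs the analysis. A pre-dose rule may exist in one of those places.
- **That the ratio is the only Tmax result.** Tmax is also reported within arms, and SAP 5.1.3.10 adds a mixed-effects model that includes the absorption rate.
- **That participants would be dropped because of their outcome.** Nothing in the SAP plans this.
- **That zeros cannot be analysed at all.** The Wilcoxon test accommodates zeros and ties.

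The defence does not supply a usable between-arm estimate. The Wilcoxon test is supplemental and its stated output is a p-value, whereas SAP 2.3 promises an estimate with an interval. For observed Tmax, that leaves only the ratio.

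**Conclusion.** The point holds in a limited form. The SAP makes the geometric mean ratio its sole between-arm estimate for Tmax. That ratio suits a time confined to sampling points poorly, and it is undefined if a pre-dose sample holds the maximum, a case that the definitions leave open and for which the SAP states no rule. If one such case arose among 20 in Arm C, the ratio would shift by a factor of 1.12 to 1.36 depending on the substitute. This assumes that 5 h is the value displaced and that the substitute lies between 0.5 and 0.01 h. A smaller Arm C would enlarge the shift.

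The consequence is minor. Tmax is one of four parameters in one secondary PK comparison, and the documents tie no decision to its ratio. The planned ratios for Cmin, Cmax and AUC0-24h are suitable, and the primary analyses are untouched.

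**What to change.** Amend SAP 3.2.11 and 5.1.3.10 as follows:

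- Keep the geometric mean ratio with 90% confidence interval for Cmin, Cmax and AUC0-24h, and remove Tmax from that list.
- For Tmax, report the median and range by arm, and the Hodges-Lehmann difference (Arm 1 minus Arm C, in hours) with its 90% confidence interval, paired with the Wilcoxon rank sum test already planned.
- State whether a pre-dose sample can define Cmax and Tmax, or point to the document that already says so.

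The rank-based estimate takes zeros and ties as they are, so nobody is altered or left out. Its limits may be coarse because many differences will be tied, which reflects the sampling times fairly. The cost is a few lines of SAP wording, with the same data and no added visits or samples.

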**5.1.3.11 CFZ-associated skin hyperpigmentation (Objective 2.3.2.12; Outcome Measures 3.2.12 and 3.2.13)**

We will compute the total color difference scores using the CIELAB color space output values, (L, a, b), from the colorimeter device. Since each reading is done in triplicate, we will use the average scores from the three readings for L, A, and b for each participant. The analysis for each anatomical locations will be separate.

The CIE76 formula for total color difference, Delta E, is given by:  $\Delta E = \sqrt{\Delta L^2 + \Delta a^2 + \Delta b^2}$

We will compare the mean change in total color difference ( $\Delta E$ ) from week 0 (entry) to each of weeks 8, 13, 26, 65 in Arm 1 vs Arm 2 at each of the following locations; (1) forehead, (2) left cheek, (3) right cheek, (4) chin in the mITT-B population. That is, for each anatomical location, we will compute the difference between  $\Delta E$  at week 0 and week 8 for each of Arm 1 and Arm 2. We will compare the differences with a t-test.

We will also compare the mean change in total color difference ( $\Delta E$ ) from week 0 (entry) to each of weeks 8, 13, 26, 65 in Arm 1 vs Arm 2 using, for each participant in the safety set, the location with the maximum change. We will compare differences between arms with a t-test.

We will compare the 'mean change in coloration score' and 'mean distress related to skin coloration score' for Arm 1 vs Arm 2 at each of weeks 0, 8, 13, 26, and 65 in the safety set.

Using subjective assessments of clinical images, we will compare the proportion of participants with each degree of skin discoloration in Arm 1 vs Arm 2 in the safety set. We will provide the point estimates together with the Pearson Klopper exact 95% confidence intervals.

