### 2.3.2 Secondary Objectives

Each is a comparison between Arm 1 and Arm 2 unless otherwise specified.

- 2.3.2.1 To compare proportion of participants who experience a favorable composite efficacy outcome at 65 weeks between Arm 1 and Arm 2 participants
- 2.3.2.2 To compare premature regimen discontinuation (tolerability) between Arm 1 and Arm 2 participants
- 2.3.2.3 To estimate and compare CFZ-associated increases in QT interval (QTcF, using the Fridericia correction)
- 2.3.2.4 To estimate and compare time to stable liquid and solid mycobacterial culture conversion
- 2.3.2.5 To compare proportion of participants with liquid and solid culture conversion at weeks 8 and 12 between Arm 1 and Arm 2 participants
- 2.3.2.6 To compare days to positivity in automated liquid mycobacterial culture over treatment time
- 2.3.2.7 To compare chest radiographic score (with specific attention to resolution of cavitary disease) between Arms from baseline to end of treatment (Arm 1, week 13; Arm 2, week 26) between Arm 1 and Arm 2 participants
- 2.3.2.8 To compare proportions of participants who experience a favorable clinical/bacteriologic treatment outcome at 65 weeks between Arm 1 and Arm 2 participants
- 2.3.2.9 To estimate cumulative relapse and recurrence proportions up to week 65 for participants on Arm 1 and Arm 2
- 2.3.2.10 To determine CFZ pharmacokinetic (PK) parameters in plasma in Arm 1
- 2.3.2.11 To compare PK parameters when CFZ is given with a loading dose in Arm 1 and without a loading dose in Arm C
- 2.3.2.12 To objectively and subjectively assess CFZ-associated skin hyperpigmentation between Arm 1 and Arm 2 participants

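### The colorimeter analysis of skin hyperpigmentation uses only the unsigned distance Delta E, so it cannot show that skin darkened; signed change in L*, a*, b* should be added

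*SAP*

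**What the plan says.** SAP 2.3.2.12 sets the objective: "To objectively and subjectively assess CFZ-associated skin hyperpigmentation between Arm 1 and Arm 2 participants". The heading of outcome measure 3.2.12 names the signed components: "Change from baseline in skin pigmentation (colorimetric L\*, a\*, b\* parameters) utilizing ambient light-independent reflectance mapping at weeks 8, 13, 26, and 65". The summaries beneath that heading, for four facial sites, use only the total color difference: "Mean change in total color difference from week 0 to each of weeks 8, 13, 26, 65 in Arm 1 vs Arm 2 at each". A further summary is formed "using, for each participant, the location with the maximum change".

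SAP 5.1.3.11 defines the metric ("The CIE76 formula for total color difference, Delta E, is given by" the square root of the summed squared changes). For the change it says "for each anatomical location, we will compute the difference between" Delta E at week 0 and at week 8 in each arm, followed by "We will compare the differences with a t-test". The second comparison takes "the location with the maximum change. We will compare differences between arms with a t-test".

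The same section compares participant-rated coloration and distress between arms, and the proportion with each degree of discoloration on clinical images. SAP 6.7 lists contrasts in total color difference with 95% CIs for outcome 3.2.12. Neither section contains a contrast in L\*, a\* or b\*.

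**The concern.** Delta E is a distance. It cannot be negative, and it discards the sign of the change in L\*, the axis on which darkening is read. The colorimeter is the objective half of an objective that asks for both objective and subjective assessment. Followed as written, the plan could report a significant colour difference without saying which way the colour moved.

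Two further consequences are possible. A modest darkening in Arm 1 may hardly move mean Delta E, because random variation on all three axes already raises it in both arms. And if both arms shared a drift in colour, the Delta E contrast would no longer follow the drug effect, whereas a difference in signed change would.

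The instruction to difference Delta E between week 0 and week 8 is a separate problem of definition: an analyst cannot tell which reference reading is meant at week 0.

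**Working it through.** **Inputs.** Planned sizes of about 110 in Arm 1 and 55 in Arm 2 (SAP 2.4). Accrual closed early, and the number available for this outcome is not stated. The documents give no SD, expected shift or power for any skin outcome, so there is no planned figure to reproduce. Assumed: normal, independent changes; SD of change 1 in L\* and 0.5 to 1.0 in a\* and b\*; Arm 2 unchanged on average; a t-test at two-sided 5%, to match the 95% CIs.

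**1. Direction.** ΔE = √(ΔL² + Δa² + Δb²). Because ΔL is squared, +d and −d give the same value. In simulation with SDs 3/1.5/1.5 and a 3-unit shift in Arm 1, mean Delta E is 4.23 for darkening and 4.23 for lightening, with power 0.84 and 0.82 (equal within simulation error).

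**2. Why small shifts are hard to see.** With a shift d in L\* only, the mean of ΔE² is σ_L² + σ_a² + σ_b² + d². For SDs 1/0.5/0.5 this is 1 + 0.25 + 0.25 = 1.50 with no shift, and 1.50 + 0.25 = 1.75 at d = 0.5. The shift enters only as its square. In the 3/1.5/1.5 setting, a true darkening of 1.5 units moves mean Delta E from 3.30 to 3.54, a difference of 0.24.

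**3. Power for signed L\*.** The standard error of the arm difference, in SD units, is √(1/110 + 1/55) = 0.165. At 0.5 SD, 0.5/0.165 = 3.03, and Φ(3.03 − 1.96) = 0.86. At 0.75 SD, 4.54 − 1.96 = 2.58, giving 0.995. Both agree with the simulation.

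**4. Power compared** (simulated, L\* shift only, 110 v 55; ranges cover the a\*, b\* SDs):

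| Shift in L\* | Signed L\* | Delta E |
|---|---|---|
| 0.5 SD | 0.85 | 0.09–0.12 |
| 0.75 SD | 0.99 or more | 0.22–0.41 |
| 1 SD | 1.00 | 0.55–0.84 |
| 1.25 SD | 1.00 | 0.89–0.99 |

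At an illustrative 67 v 33, Delta E has 0.35–0.61 at 1 SD and 0.91–0.99 at 1.5 SD.

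**5. When a\* and b\* also move** (shifts in L\*/a\*/b\*; Delta E v signed L\*):

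| SDs | −0.5/+0.5/+0.5 | −0.3/+0.7/+0.5 |
|---|---|---|
| 1/0.5/0.5 | 0.84 v 0.86 | 0.93 v 0.44 |
| 1/1/1 | 0.37 v 0.85 | 0.42 v 0.44 |

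Neither measure is stronger throughout.

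**6. Shared drift (illustration only).** Hold the true arm difference at 1 SD of darkening and lighten both arms by 0.5 SD. The net shifts are then −0.5 and +0.5, and Delta E rejects 5% of the time, which is no signal. With 0.7 SD of drift the net shifts are −0.3 and +0.7, and mean Delta E is larger in Arm 2 (1.26 v 1.13). Signed L\* keeps power 1.00 in both cases.

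**7. The week 0 wording.** With entry as the reference, ΔE at week 0 is √(0 + 0 + 0) = 0, so the subtraction adds nothing. With any other reference, the result is a difference between two distances from that reference, which is not the distance the skin colour moved. No other reference is stated.

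**The case against.** The strongest reply is that Delta E is a reasonable omnibus measure. Outcome 3.2.12 names all three axes, nothing in the documents confines the change to L\*, and step 5 shows Delta E ahead when a\* and b\* carry much of the change. That stands. A reader might infer that signed L\* should replace Delta E or rank above it; the documents do not support this.

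A reader might also infer that hyperpigmentation is tested only through Delta E. It is not: SAP 5.1.3.11 also compares image-graded discoloration and two participant scores. These do not supply the missing direction, however. The coloration score runs from none to most significant, the images are graded by degree of discoloration, and no darker or lighter anchor is given for either.

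Nor is it shown that choosing the maximum-change location adds noise. That comparison is unsigned too, but at 0.5 SD its simulated Delta E power was 0.11–0.22, no lower than for a single location.

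Nothing in the documents suggests that the arms drift or move in opposite directions, so step 6 shows only what could happen. Finally, this is a secondary outcome reported as estimates with CIs. SAP section 6 lists minimum contents and leaves table detail to a separate implementation plan, so component summaries are not ruled out. But they are not specified either.

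**Conclusion.** The point holds for the colorimeter analysis. As specified, it cannot distinguish darkening from lightening, although the objective is hyperpigmentation and the heading of 3.2.12 names L\*, a\* and b\*. This follows from the formula and needs no assumption.

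The size of any power loss cannot be fixed from the documents. A reader might infer that Delta E generally loses most of the power. The calculations support that only for assumed shifts confined to L\* and no larger than about 0.75 SD at the planned size. The gap has nearly closed by 1.25 SD, and it can close or reverse when a\* and b\* move as well.

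The week 0 instruction is redundant if entry is the reference and undefined otherwise. No primary conclusion is affected.

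**What to change.** In SAP 5.1.3.11 and 6.7, add the between-arm difference in signed change from week 0 in L\*, and likewise in a\* and b\*, with 95% CIs, at the same weeks and facial locations. Report these alongside Delta E, which stays as the measure of total change.

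In 5.1.3.11, replace the instruction to difference Delta E between visits with a statement that Delta E is computed from the week 0 reading to each visit and is not differenced again.

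The cost is a few more contrasts and table rows from readings already collected. No new measurements or visits are needed.

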The primary efficacy analysis will be a superiority comparison of time to liquid culture conversion through 12 weeks in Arm 1 compared with Arm 2. The primary safety analysis will estimate and compare the proportions of participants who have a Grade 3 or higher safety event that is at least one grade higher than baseline at any time during the study. Important secondary analyses include 65-week favorable composite efficacy outcome, including cumulative relapse proportion versus 6-month SOC controls; and safety and tolerability (regimen discontinuation) in Arms 1 and 2.

The primary completion date for A5362 is the final visit date that is included in the primary safety analysis, which will occur approximately 65 weeks after the last participant enrolls. With the early closure to accrual in June 2023, the primary analysis report forming the basis of the primary manuscript will occur earlier than the original planned timepoint. We will prepare the primary analysis report using data collected at visits up to and including the date when the last enrolled participant completes the week 26 study visit. We will later conduct a supplemental analysis using data through week 65, which will form the basis of a secondary manuscript and the clinicaltrials.gov requirements.

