## **2.3 Study Objectives**

This Primary SAP addresses the following primary and secondary objectives listed in the study protocol. We address other study objectives outlined in the protocol in subsequent secondary analysis plans.

We will analyze the primary efficacy objective below (2.3.1.1) using a superiority framework based on a one-sided 0.05 alpha level test. For analyses of other objectives, we will present estimates of the parameter of interest alongside their respective two-sided confidence intervals, as specified in Section 5.

We will finalize all analyses for the primary analysis report once the last enrolled participant has completed the week 26 study visit and all queries have been resolved.

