## 2.4 Overview of Sample Size Considerations

We plan to enroll a total of 185 participants; approximately 110 in Arm 1, 55 in Arm 2, and 20 in Arm C. We estimate that we will have at least 90% power to detect an effect between Arm 1 and Arm 2 with respect to the primary efficacy outcome. We assume 70% culture conversion by week 12 in Arm 2 and a hazard ratio of 1.8. We use a 2:1 allocation ratio and assume that 10% of participants will have unevaluable culture conversion results.

For the primary safety outcome, we will compare proportions of participants with any Grade 3 or higher adverse events (AE) between Arms. Table 10.4-2 from the study protocol (copied below) gives the power we would have to detect that Arm 1 is inferior to Arm 2 assuming a two-sided type 1 error of 0.10, 10% probability of developing an AE in the SOC Arm, and varying probabilities (15-30%) of developing an AE in experimental Arm. We also provide the 90% confidence interval (CI) width for the comparison.

Protocol Table 10.4-2

Power	N1	N2	N	Arm 1 Proportion with $\ge$ Grade 3 AE	Arm 2 Proportion with $\ge$ Grade 3 AE	Two-sided type 1 error	90% CI Width
0.13	100	50	150	0.15	0.10	0.10	0.210
0.36	100	50	150	0.20	0.10	0.10	0.218
0.64	100	50	150	0.25	0.10	0.10	0.225
0.85	100	50	150	0.30	0.10	0.10	0.230

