## 6.7 Secondary Outcome Measures

- Proportions in each arm, and difference in proportions with corresponding confidence interval for outcome measures 3.2.1A and B, 3.2.2, 3.2.5, 3.2.6, 3.2.9, 3.2.10.
- Contrasts that estimate the difference between mean change in QTcF scores between Arm 1 and Arm 2 from screening to weeks 2, 8, and 13 with corresponding 95% confidence intervals (outcome measure 3.2.3.1)
- Odds ratio and 95% confidence interval from proportional odds model for outcome measures 3.2.3.2 and 3.2.3.3. If proportional odds model does not hold, then difference in proportions for categories QTcF  $\geq 480$  ms and QTcF  $\geq 500$  ms between arms with corresponding 95% confidence intervals.
- Kaplan-Meier curves of time to culture conversion in liquid media, and solid media, censored at 26 weeks (outcome measure 3.2.4).
- Hazard ratio and 95% confidence intervals for time to culture conversion in liquid media, and solid media, censored at 65 weeks (outcome measure 3.2.4).
- Hazard ratio and 95% confidence intervals for time to positivity in liquid media at each time point. If proportional hazards does not hold, then we will report log-rank test. Side-by-side box plots of time to positivity (Days) at each time point (weeks 1, 2, 3, 4, 6, 8, 0, 12) (outcome measure 3.2.6)
- Estimates for changes in chest x-ray score in each arm from screening to EOT, and estimate of difference in change with 95% confidence interval (outcome measure 3.2.7)
- Contrasts that estimate the difference with corresponding 95% confidence interval between Arm 1 and Arm 2 for the change in total skin hyperpigmentation color difference from week 0 to each of weeks 8, 13, 26, and 65 at each of the following locations; (1) left cheek, (2) right cheek, (3) forehead, (4) chin, (5) using the location with the maximum change in total skin hyperpigmentation color difference. (outcome measure 3.2.12)
- Contrasts that estimate the difference in mean subjective 'change in coloration score' at each of weeks 0, 8, 13, 26, and 65 in Arm 1 vs Arm 2 with corresponding 95% confidence intervals (outcome measure 3.2.13)  
Contrasts that estimate the difference in mean subjective 'distress to skin coloration' score at each of weeks 0, 8, 13, 26, and 65 in Arm 1 vs Arm 2 with corresponding 95% confidence intervals (outcome measure 3.2.12)

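### Separate t-tests of facial colour change at each visit lose precision at week 65 in the early-cut primary report; a repeated-measures model recovers part of it, and a four-site mean is worth adding as a further summary

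*SAP*

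**What the plan says.** SAP outcome 3.2.12 defines the colorimeter outcome at the left cheek, right cheek, forehead and chin, and at each participant's location of greatest change, for weeks 8, 13, 26 and 65.

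SAP 5.1.3.11 follows that definition. It states: "The analysis for each anatomical locations will be separate". The arms are compared by t-test at each site and visit, and again "using, for each participant in the safety set, the location with the maximum change". Triplicate readings within a site are averaged. The section gives no average over sites and no model over visits.

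SAP 6.7, which lists contents of the primary analysis report, asks for: "Contrasts that estimate the difference with corresponding 95% confidence interval between Arm 1 and Arm 2 for the change in total skin" colour at all four weeks, for the four sites and the maximum site. It names no model.

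SAP 2.1 places the data cut at the final enrollee's week 26 visit, in a sentence that begins: "We will prepare the primary analysis report using data collected at visits up to and including the date when the last enrolled participant". A supplemental analysis of data through week 65 follows later.

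For QTcF, another repeatedly measured outcome, SAP 5.1.3.2 specifies a GEE with time-by-treatment terms and a linear mixed model.

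**The concern.** A t-test at one visit uses only participants measured at that visit. That costs little when nearly everyone has a value, but the primary report is cut 39 weeks (65 − 26) before the last participant could reach week 65. Later enrollees contribute up to three earlier colour readings that are correlated with the missing one, and the week 65 t-test uses none of them. The week 65 intervals listed in SAP 6.7 are therefore wider than the collected data require.

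A second, smaller matter is the cross-site summary. If clofazimine darkens the whole face, an average over sites is steadier than the largest of four noisy readings, and the plan has no such average.

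The precision of one secondary safety and tolerability description is at stake. No primary conclusion depends on it.

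**Working it through.** **Inputs from the documents.** SAP 2.4 plans "approximately 110 in Arm 1, 55 in Arm 2, and 20 in Arm C"; Arm C is not in this comparison. It adds: "We use a 2:1 allocation ratio and assume that 10% of participants will have unevaluable culture conversion results". That leaves 99 v 49.5, and the safety power table in the same section uses 100 v 50, which I use here. The number actually enrolled is not given.

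**The plan's own figure.** There is none for colour: no SD, effect size or correlation. The stated power of at least 90% concerns primary efficacy and does reproduce. SAP 2.4 says: "We assume 70% culture conversion by week 12 in Arm 2 and a hazard ratio of 1.8". SAP 2.3 specifies analysis "using a superiority framework based on a one-sided 0.05 alpha level test".
- Arm 1 conversion = 1 − 0.30^1.8 = 0.885
- Events = 99 × 0.885 + 49.5 × 0.70 ≈ 122
- Power = Φ(ln 1.8 × √(122.3 × 2/9) − 1.645) = 0.922

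This supports the sample sizes but says nothing about colour. Everything below rests on assumed correlations and effects.

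**Step 1: the gain from modelling visits.** Let m be the fraction with no week 65 value, equal in both arms, and R² the share of week 65 variance explained by the earlier visits. Relative to the t-test, the variance of the week 65 contrast is 1 − mR². With three earlier visits and a common visit correlation ρ, R² = 3ρ²/(1 + 2ρ). At ρ = 0.5 this is 0.75/2 = 0.375; at ρ = 0.7 it is 1.47/2.4 = 0.6125.

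| m | ρ = 0.5 | ρ = 0.7 |
|---|---|---|
| 0 | no change | no change |
| 10% | √(1 − 0.0375) = 0.981 (SE down 2%) | √(1 − 0.0613) = 0.969 (down 3%) |
| 20% | √(1 − 0.075) = 0.962 (down 4%) | √(1 − 0.1225) = 0.937 (down 6%) |
| 50% | √(1 − 0.1875) = 0.901 (down 10%) | √(1 − 0.3063) = 0.833 (down 17%) |

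If only one earlier visit carries the information, R² = ρ² and the gains shrink: 3 to 5% at m = 20% and 6 to 13% at m = 50%.

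**Which m is plausible.** The documents do not give the pace of accrual. If accrual were uniform over A weeks with no other losses, m = 39/A. Then 50% corresponds to 78 weeks of accrual and 20% to 195 weeks.

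**Step 2: four-site mean against maximum, diffuse change.** Assume a half-SD shift at every site, 100 v 50, two-sided 0.05 and site correlation r. The SE for one site is √(1/100 + 1/50) = 0.173 SD. The mean of four multiplies the SD by √((1 + 3r)/4). The maximum multiplies it by √(r + 0.492(1 − r)), where 0.492 is the variance of the largest of four independent standard normals. Both keep the full half-SD shift. Power = Φ(0.5/(0.173 × factor) − 1.96). A single site has 82%.

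| r | Maximum: factor, power | Mean: factor, power | Gap (points) |
|---|---|---|---|
| 0.3 | 0.803, 95% | 0.689, 99% | 4 |
| 0.5 | 0.864, 92% | 0.791, 95% | 4 |
| 0.7 | 0.921, 88% | 0.880, 91% | 3 |
| 0.9 | 0.974, 84% | 0.962, 85% | 1 |

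Gaps are taken before rounding. Simulated t-tests agree to within about a point.

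**Step 3: the same comparison, focal change.** Put 0.8 SD at one site and nothing elsewhere. The mean then carries a shift of 0.8/4 = 0.2 SD. At r = 0.5 its power is Φ(0.2/(0.173 × 0.791) − 1.96) ≈ 31% (30% by simulation). The simulated maximum has 58%. The order reverses.

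**The case against.** The strongest reply is that the plan does what its outcome definition says. SAP 3.2.12 defines the outcome at four named sites and at the worst site. The true replicates, the triplicate readings, are already averaged, so a four-site mean is a further estimand. SAP 2.3 says that objectives other than primary efficacy are reported as estimates with intervals, so the power of one pooled test is not the stated purpose. All of this stands, and it is why the mean is proposed only as an addition.

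A reader might infer that the plan wastes the four sites, loses substantial power, and should make the mean its main comparison with the maximum demoted to description. The documents do not support that. They give no SD, effect or site correlation. Against the maximum, which the plan already has, the mean gains 1 to 4 points if the change is diffuse and loses heavily if it is focal.

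A reader might also infer that visit-by-visit testing wastes data throughout. It does not: with complete data, a visit-specific contrast from a model with unstructured covariance gains essentially nothing. Averaging over visits would ask a different question, since Arm 1's planned treatment ends at week 13 and week 65 is a year later.

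Three further points stand. A difference of two means is itself a contrast, so SAP 6.7 does not strictly demand a model. The later supplemental analysis restores most week 65 values. Pigmentation is also described by participant-rated scores and graded clinical images, so the maximum is the only cross-site summary of the colorimeter data, not of pigmentation as a whole.

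What the reply does not answer is the week 65 comparison in the primary report. Values will be missing there by design, and the earlier readings of those participants go unused.

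**Conclusion.** The point holds as a modest gain in precision. At the primary report, modelling the visits jointly would lower the week 65 standard error by about 4 to 6% if 20% lack that visit and 10 to 17% if 50% do. This assumes a common visit correlation of 0.5 to 0.7 and equal missingness in the arms. In the supplemental analysis the gain is much smaller: 2 to 3% at 10% missing, a fraction borrowed from the SAP's allowance for unevaluable cultures.

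The loss is one of precision. Missing values caused by the calendar cut do not in themselves bias the t-test, and the plan should not be read as biased on this ground.

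A four-site mean is sound as an added prespecified summary. Whether it beats the maximum depends on whether pigmentation is diffuse or focal, which the documents do not settle.

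**What to change.** In SAP 5.1.3.11, replace the visit-by-visit t-tests with one repeated-measures model per colour outcome (each site and the maximum site), with arm, week, arm-by-week interaction and unstructured covariance. Report the arm contrast with 95% CI at weeks 8, 13, 26 and 65. This supplies the estimates listed in SAP 6.7 and accords with the repeated-measures approach to QTcF in SAP 5.1.3.2.

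Add the four-site mean, fitted by the same model, as a further prespecified summary in SAP 3.2.12, 5.1.3.11 and 6.7. Leave the site-specific and maximum-site results at their current standing.

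Two wording matters in SAP 5.1.3.11 need settling so that the model has a defined response and population. ΔE is already a difference from baseline, yet the text takes a difference between ΔE at week 0 and at week 8. The site-level analysis also uses an mITT-B population that SAP 4.1.1 does not define, whereas the maximum-site analysis uses the safety set.

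The cost is a short SAP edit, including one added line in the outcome definition, and slightly more analysis work. No new data are needed.
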